9.4.3 Other Analyses

PK, Pd, and biomarker exploratory analyses will be specified in the Integrated Analysis Plan finalized before database lock. Integrated analyses across studies, such as the population PK analysis and Pd analyses will be presented separately from the main clinical study report.

9.4.4 Sequence of Analyses

This is an exploratory study.

The SMC will review available data during study conduct. The cut off for dose escalation assessments in Part A by the SMC will be triggered by the completion of the DLT period (or discontinuation) of the last participant in the respective dose escalation cohort. If enrollment of the last participant in a dosing cohort is delayed, the SMC may decide on available data for enrollment and dose of the next dosing cohort before all participants in a cohort have completed Cycle 1. In these cases, cut-off can be earlier (after DLT period of the first 2 participants is finished or they experienced a DLT).

For Part A, the cut off for an exploratory interim analysis of the safety, available PK, available Pd and preliminary antitumor activity data from the complete dose escalation will be triggered when all participants enrolled in the dose escalation:

- Had the first on-study intervention tumor assessment or
- Experienced death or
- Withdraw for any reason

whichever comes first.

In Part B, an interim analysis will be conducted after 15 participants who are treated at the same dose are evaluable for response. If at this interim analysis, the dose is increased, one additional interim analysis may occur after 15 participants are treated on the new dose and are evaluable for response. Additionally, there are SMCs planned after 3, 6, and in the following every 6 participants have finished the DLT period. For all SMCs the analyses necessary for these SMCs will be conducted (as described in the integrated analysis plan for SMCs).

Additional analysis during the study might be conducted, e.g., for publication purposes.

The primary analysis will be performed once all participants have completed the second response evaluation (or discontinued prematurely).

Follow-Up analyses to further efficacy and safety data will be done once the End of Study has been reached.

The preliminary food effect will be evaluated at the time of interim analysis in the available participants in Part B. The results will be indicative of whether to evaluate further participants on food effect or stop the food effect evaluation.

More details will be described in the Integrated Analysis Plan.

10 Safety Monitoring Committee

The SMC consists of core (internal and external voting) members for the Sponsor (Global Patient Safety Product Leader [Chair], Medical Responsible, Clinical Pharmacologist and Biostatistician), the Coordinating Investigator, and the Medical Monitor of the Contract Research Organization. Ad hoc members may be invited as needed.

During the dose-escalation Part A of the study, the SMC will evaluate the safety data (including DLTs) and available PK and Pd data, as defined in the SMC charter, in order to make recommendations on the dosing of the next participant cohort.

A Bayesian two-parameter logistic regression model ([Neuenschwander et al. 2008](#)) will be used to assist the SMC with dose selection. Further details on the Bayesian model are provided in Section [9.4.2](#) and [Appendix 10 Description of the Bayesian Dose Escalation Model0](#).

The SMC may choose a different dose than suggested by the Bayesian escalation model (however, not higher than 50 mg).

Based on the observed toxicity profile and available PK and Pd, dose level(s) that are different than the prespecified doses may be recommended by the SMC. However, escalation may not proceed to any dose higher than 50 mg. In case escalation should proceed to doses higher than 50 mg, an amendment will be submitted. Based on observed toxicity profile, PK and Pd data, the SMC may recommend changing the dosing regimen as specified in Section [4.1](#).

The planned cohort size is 3 participants at a given dose. Parallel screening and enrollment of participants will allow eligible participants to enroll, the cohort size may therefore increase to 4 participants. Any additional participants enrolled in the study at a given dose, will complete all study procedures and assessments as per protocol. Based on the safety, PK and Pd data (if available) collected from the participants in a cohort, the SMC may recommend that no further participants are required in a cohort before the planned cohort size is reached. In cases where enrollment of the last participant in a dosing cohort was delayed, the SMC may decide (based on available data) upon enrollment and dose for the next dosing cohort before all participants in a cohort have completed the DLT period. For this participant, the SMC will consider all available data (and any subsequent emerging data at a subsequent meeting). An ad-hoc meeting will be convened if this participant experiences a DLT.

Participants who did not experience a DLT and who either did not receive at least 80% of the planned cumulative dose of treatment during the DLT period, or at least 80% of the planned

administrations, or did not complete the DLT observation period will not be considered for DLT evaluation and in the Bayesian model. An SMC meeting with selection of dose for next cohort will also be held if not all participants in a cohort are evaluable (e.g., if a participant missed more than 20% of treatment in the first cycle for any reason other than a DLT).

The SMC might modify the schedule of PK and Pd sampling based on emergent data. However, the total blood volume taken for PK and Pd samples will not exceed blood volume described in this protocol or the Laboratory Manual.

For the expansion part of the study, the SMC will monitor the safety of M3258 at the recommended dose with dexamethasone and may recommend by consensus on continuation at the same dose, change in dose (only to doses declared safe by SMC in monotherapy), modifications of the study protocol, or stop of expansion cohort. The same DLT criteria as for the monotherapy dose escalation will apply. Additional safety stopping rules apply as outlined in Section 7.1.

The SMC will evaluate the safety of the combination therapy after 3, 6, (safety run-in) and subsequently every 6 participants finished their DLT period or discontinued, unless a change in dosing has occurred. In case the dosing in the expansion cohort was changed, the next SMC will be held after the next 3 participants have finished the DLT period or discontinued and then the SMCs are scheduled every 6 participants having finished the DLT period or discontinued.

For SMCs in the safety run-in and the first SMC after a dose change, dosing of new participants can only start after SMC has decided to proceed (including on what dose). For all other SMCs there is no pause in enrollment.

The SMC decisions in expansion cohort will also be supported by a two-parameter Bayesian logistic regression model. For details on the model, see Section 9.4.2.

The SMC may modify the frequency of meetings as deemed appropriate during the study.

After the evaluation of the food effect in 15 participants in Part B, the SMC will take the decision whether to increase the number of participants which are to be included in the food effect evaluation.

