The dose-expansion phase of this study is designed to obtain additional safety, tolerability, PK, Pd and preliminary clinical activity data of M3258 in combination with dexamethasone.

The SMC decisions in the expansion phase will also be supported by Bayesian modeling. If data obtained during the safety run-in of Part B indicate that a higher dose than the RDE may be tolerated when M3258 is administered in combination with dexamethasone, then a careful escalation beyond the monotherapy RDE in combination with dexamethasone can be recommended in dosing steps of maximum 25% increases in Part B. SMC will review all available data to provide recommendations on the next dose level.

Unacceptable toxicity in the expansion cohort is defined as AEs that meet the DLT criteria (as defined in Section 6.6) regardless of when they occur during treatment; stopping rules for unacceptable toxicity for participants treated at the same dose are detailed in Section 7.1.

If at any time in the expansion cohort, the number of unacceptable toxicity events indicate that there is a risk of safety to the participants (i.e., if defined boundaries are met, see Section 7.1), accrual to the cohort will be paused and the SMC will meet to review the data, also considering feedback from investigators, to determine if further enrollment should be halted. In this case, the SMC will decide whether participants who are still on treatment and are tolerating the treatment should continue treatment or whether treatment should be reduced or withdrawn. The Health Authorities (HA) will be notified of the SMC decision.

If a situation of unacceptable toxicity occurs that does not meet the defined boundaries for stopping criteria (as outlined in Section 7.1), the SMC will decide whether the dose for newly enrolled participants should be lowered (including to what dose). In case dosing is de-escalated for toxicity in the expansion cohort, only 3 participants will be treated initially with the new dose; enrollment of additional participants will pause until the SMC has evaluated the safety of this cohort. Expansion cohort SMC meetings will also be supported by the results of a Bayesian logistic 2 parameter regression model.

When 15 participants treated at the same dose are evaluable for response (as defined in Section 8.1), according to IMWG, an interim analysis will be performed. At that time the following decision will be made:

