9.4.1 Efficacy Analyses

Endpoint	Statistical Analysis Methods
Primary	No primary efficacy endpoint is specified

Secondary	Will be specified in the Integrated Analysis Plan finalized before database lock. In general, continuous variables will be summarized using number of participants (n); mean, standard deviation; median, 25 th Percentile to 75 th Percentile (Q1-Q3), minimum, and maximum. If there are less than 5 observations available, only mean and the observed data will be given. Categorical variables will be summarized using frequency counts and percentages. The calculation of proportions will be based on the number of participants in the analysis set of interest, unless otherwise specified in the study Integrated Analysis Plan. Kaplan-Meier estimates (product-limit estimates) will be presented for the analysis of PFS and OS together with a summary of associated statistics (median survival time, 6-, 12-month survival rate estimates and estimates for every 6 months thereafter if applicable) including the corresponding 2-sided 95% CIs.
Tertiary/Exploratory	Will be specified in the Integrated Analysis Plan finalized before database lock.

CI = Confidence Interval; PFS = Progression-Free Survival; OS = Overall Survival.

In Part B, a two-stage design with an interim analysis after 15 participants treated on the same dose and evaluable for response is foreseen. If less than 3 responses are seen out of 15 participants evaluable for response, the expansion cohort is stopped for futility or dose is increased. This gives a probability of falsely stopping the study if the drug were effective (assuming an ORR of 35%) of 6%, while already correctly stopping the study if the drug is not sufficiently effective (assuming an ORR of 15%) of 60%. Else the study continues, until 30 participants are evaluable for response.

At this interim analysis there is the possibility to:

- If ≥ 3 responders are seen (in participants treated on the same dose) and there are no safety concerns, continue the study on the same dose until 15 additional participants are treated at the same dose who are evaluable for response according to IMWG, or
- If < 3 responders are seen, either:
 - Stop the study for futility, or

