- Number of dosing days (in days) as defined by (date of last dose of study drug–date of first dose of study drug–sum of days with dose interruption +1)
- Total number of cycles received at least 80% of planned dose as defined sum of cycles with received dose \geq 80% of planned dose
- Number and percentage of participants with at least one dose reduction will be presented.

A listing will be provided for all administrations of participants (date and dose of administration) including planned regimen and dose.

14**Efficacy Analyses**

The following analyses will be performed based on the SAF analysis set, by regimen and dose (in increasing order) and summarized. In case the received cumulative dose of a participant is higher than planned cumulative dose the participant will not be considered in efficacy analyses.

14.1**Overall Response**

Overall response (OR) will be assessed based on reported overall responses at different evaluation time points from the treatment start date in accordance to IMWG response criteria, taking requirements for confirmation into account as detailed below.

OR is defined as a confirmed (2 consecutive assessments made at any time before the institution of any new therapy) Best Overall Response of sCR, CR, VGPR, or PR according to IMWG response criteria.

Participants will be considered evaluable for response in the analysis set if they have at least two on-treatment assessment of IMWG response criteria other than Not Evaluable (NE).

Except for participants who have at least one on-treatment assessment of IMWG response criteria and who receive anti-tumor treatments other than the study treatment, die, progress or withdraw for any reason prior to reaching confirmed sCR, CR, VGPR or PR. These will be considered as non-responders in the assessment of OR.

Each evaluable participant will have an objective response status (0: 'no OR'; 1: 'OR') The participants who are not evaluable will be considered Not Evaluable (NE).

OR rate (ORR) is the proportion of participants with OR in the participants evaluable for response in the analysis set.

The ORR by regimen and dose and in summary will be calculated along with the two-sided 95% CI using the Clopper-Pearson method (exact CI for a binomial proportion as computed by default by the SAS FREQ procedure using the EXACT option).

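### A response first seen at a participant's latest assessment is scored as a non-response, because the protocol's efficacy cut-off is the second evaluation and confirmation needs two

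*Protocol*

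**What the plan says.** **Confirmation.** SAP 14.1: "OR is defined as a confirmed (2 consecutive assessments made at any time before the institution of any new therapy". Protocol 8.1 and the notes to its Table 16 also require two consecutive assessments. Under the Schedules of Activities (protocol 1.3), disease assessment falls on Day 1 of each cycle, so the on-treatment evaluations are C2D1, C3D1, C4D1 and so on.

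**Evaluability.** SAP 14.1: "Participants will be considered evaluable for response in the analysis set if they have at least two on-treatment assessment of IMWG response criteria" (not-evaluable results excluded). Each such participant then has a binary status, OR or no OR. One assessment is enough for a participant who progresses, dies, withdraws or starts other anti-tumor treatment before a confirmed response; that participant is a non-responder.

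**Cut-offs.** Protocol 9.4.4: "The primary analysis will be performed once all participants have completed the second response evaluation (or discontinued prematurely". The Part A exploratory interim is triggered when all participants "Had the first on-study intervention tumor assessment or" died or withdrew.

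**Part B interim.** Protocol 4.1 starts it as follows: "When 15 participants treated at the same dose are evaluable for response (as defined in Section 8.1". Section 8.1 lists which results count as a response at the interim (PR or better), but gives no evaluability or minimum-follow-up rule. Protocol 9.4.1 sets the decision: "If less than 3 responses are seen out of 15 participants evaluable for response", stop for futility or increase the dose. The stated probability of stopping is 6% at a true ORR of 35% and 60% at 15%.

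**The concern.** Take a participant with stable disease at C2D1 and PR at C3D1 who remains on treatment. The PR can only be confirmed at C4D1. At a cut-off set by the second evaluation this person is evaluable and has no confirmed response, so the only available code is no OR. Nothing in either document asks the team to wait for C4D1.

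Two results are at stake. The ORR at the protocol's primary analysis is too low for participants whose follow-up ends there. And if the same rule governs the Part B interim, a drug with an eventual ORR of 35% falls below 3 of 15 more often than planned, leading to a stop or an unneeded dose change.

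**Working it through.** **1. The plan's own figures.** P(fewer than 3 of 15) = Σ C(15,k) pᵏ(1−p)¹⁵⁻ᵏ for k = 0, 1, 2.

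- p = 0.35: 0.0016 + 0.0126 + 0.0476 = 0.0617, or 6.2% (stated 6%).
- p = 0.15: 0.0874 + 0.2312 + 0.2856 = 0.6042, or 60.4% (stated 60%).

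Both reproduce. They are plain binomial figures that treat all 15 outcomes as settled.

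**2. Who is miscoded when data end at the second evaluation (C3D1).**

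| First PR or better | Confirmable at | Code at C3D1 |
|---|---|---|
| C2D1 | C3D1 | OR, if it holds |
| C3D1 | C4D1 | no OR |
| C4D1 or later | C5D1 or later | no OR |

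At the Part A exploratory cut-off, a participant with only C2D1 cannot have a confirmed response. Earlier enrollees have more assessments at any cut-off, so the loss falls mainly on recent ones.

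**3. Bounds for the interim.** Let f be the share of eventual confirmed responses first seen after the first evaluation. The documents do not give f. If all 15 had exactly two assessments, the visible ORR would be 0.35 × (1 − f):

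| f | Visible ORR | P(fewer than 3 of 15) |
|---|---|---|
| 0% | 0.350 | 6.2% |
| 5% | 0.3325 | 8.0% |
| 10% | 0.315 | 10.3% |
| 20% | 0.280 | 16.5% |
| 30% | 0.245 | 25.0% |
| 50% | 0.175 | 49.7% |

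This is an upper bound, because enrollment is staggered. With only 5 of the 15 at minimum follow-up and the other 10 fully observed, the figures are 7.4%, 8.7%, 10.2% and 13.7% at f = 10%, 20%, 30% and 50%.

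**4. Staggered entry.** Simulation assumptions: 28-day cycles; Poisson accrual at 1, 2 or 4 per month; enrollment pauses after participants 3 and 6 for the safety run-in; eventual confirmed ORR 35%; confirmation at the assessment after the first response; cut-off when the 15th participant reaches the second assessment. The one-assessment exception is not modelled. Ranges run from 1 to 4 enrolled per month.

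| Share of responders first seen at evaluation 1/2/3/4 | Two-assessment rule | With the pending rule proposed below |
|---|---|---|
| 100% | about 6% | about 6% |
| 90/10% | about 6–7% | about 6% |
| 60/25/10/5% | about 9–14% | about 7–8% |
| 40/30/20/10% | about 11–21% | about 8–11% |

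**5. The other side of the rule.** At a true ORR of 15%, late responses are missed as well. Correct stopping rises from 60% to about 65–79% under the two slower patterns (the upper end is without the run-in pauses).

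**The case against.** - **The SAP rule and the futility rule never operate together.** The two-assessment rule is only in the SAP, and SAP version 2.0 was adapted after the trial stopped without Part B. Applying it to the Part B interim is an inference. This stands. What the protocol itself shows is a trigger resting on an undefined term.
- **The 6% may be correct as written.** If 35% means ORR confirmed by the cut-off, the stated figure is exact. This stands, and the protocol does not say which ORR is meant.
- **The response timing and accrual are assumed.** True. Four per month is optimistic for a study that SAP section 7 says was stopped for lack of enrollment. At one per month the excess is about 0–5 points across the patterns.
- **The primary-analysis effect is softened.** The current SAP runs its single primary analysis at the end of the trial, tabulates confirmed and unconfirmed best response, and lists every IMWG assessment. The protocol adds an End of Study follow-up analysis. These reduce the effect on the primary analysis but do not help the interim.
- **Early stopping is a stated trade-off.** Protocol 9.2 says the interim timing balances information against sparing participants an inefficient treatment. That is a reason to show both error rates under the rule actually used.

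A reader might go further in two ways that the documents do not support. One is that no response can be confirmed by these cut-offs; a response seen at C2D1 is confirmable at C3D1. The other is that choice of the recommended dose for expansion is harmed. That choice is an integrated committee review whose named endpoints include LMP7 activity and M-protein or light-chain change, neither needing IMWG confirmation, and the committee's analysis plan places overall response out of scope.

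**Conclusion.** The point holds in limited form. The protocol's primary cut-off, combined with the SAP's binary coding, scores a still-treated participant with a newly seen PR or better as a non-responder. The direction of the bias in ORR is certain (downward). Its size depends on how many responses first appear after the first evaluation, which the documents do not state.

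For the Part B interim, the firm defect is that evaluability is referred to a section that does not define it. The excess over 6% (about 6–7% for fast responses, about 9–21% for slower ones) is conditional on three things: the SAP rule being used there, 35% meaning eventual confirmed ORR, and the assumed timing and accrual. It would be wrong to conclude that the 6% is miscalculated, or that the rule always ends the cohort: at the first interim, fewer than 3 responders also permits a dose increase. At a second interim the only option is to stop.

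**What to change.** 1. In protocol 8.1 and SAP 14.1, define evaluable for response so that a participant on treatment whose latest assessment is an unconfirmed PR or better is pending until the next scheduled assessment, and is not coded no OR.
2. In protocol 9.4.4, hold the interim and primary cut-offs for that one assessment where any participant is pending.
3. Label any Part A efficacy output at the first-assessment cut-off as unconfirmed.
4. In protocol 9.4.1, state that the 6% and 60% refer to ORR confirmed by the cut-off.

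**Cost.** The change is wording, plus a delay of up to about one cycle when someone is pending. No enrollment pause is stated for the interim, so a 28-day hold (28/30.4375 = 0.92 month) at 1–4 per month could add about 1–4 participants before a futility decision. The fix does not recover responses first seen after the hold, so about 6–11% remains under the same assumptions.

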Appendix 1 Abbreviations

ADL	Activity of Daily Life
AE	Adverse Event
AESI	Adverse Events of Special Interest
ALT	Alanine Aminotransferase
ANC	Absolute Neutrophil Count
AST	Aspartate Aminotransferase
AUC	Area under the Concentration-Time Curve
BED	Biologically Effective Dose
CL/f	Apparent Total Body Clearance
CLss	Clearance at Steady State
C _{max}	Maximum Observed Concentration
CR	Complete Response
CSR	Clinical Study Report
(e)CRF	(electronic) Case Report Form
CT	Computed Tomography
CV	Coefficient of Variation
DLT	Dose-Limiting Toxicity
DOR	Duration of Response
ECG	Electrocardiogram
ECOG	Eastern Co-operative Oncology Group
EDC	Electronic Data Capture
FDA	Food and Drug Administration
FiH	First in Human
FLC	Free Light Chain
FSH	Follicle-Stimulating Hormone
GCP	Good Clinical Practice
G-CSF	Granulocyte-Colony Stimulating Factor
GI	Gastrointestinal
HA	Health Authorities
HIV	Human Immunodeficiency Virus
CCI	[REDACTED]
HR	Hazard Ratio

HRT	Hormone Replacement Therapy
IB	Investigator's Brochure
ICF	Informed Consent Form
ICH	International Council for Harmonisation
IEC	Independent Ethics Committee
IFE	Immunofixation Electrophoresis
IMiD	Immunomodulatory Imide Drug
IMWG	International Myeloma Working Group
INR	International Normalized Ratio
IRB	Institutional Review Board
LMP7	Large Multifunctional Protease 7
MM	Multiple Myeloma
M-protein	Monoclonal Paraprotein
MR	Minimal Response
MRD	Minimal Residual Disease
MRI	Magnetic Resonance Imaging
MTD	Maximum Tolerated Dose
MUGA	Multigated Acquisition
NA	Not Applicable
NCI- CTCAE	National Cancer Institute Common Terminology Criteria for Adverse Events
NGS	Next-Generation-Sequencing
NSAIDs	Nonsteroidal Anti-inflammatory Drugs
OR	Overall Response
ORR	Overall Response Rate
OS	Overall Survival
PBMC	Peripheral Blood Mononuclear Cell
PC	Plasma Cell
Pd	Pharmacodynamics
PD	Progressive Disease
PFS	Progression-Free Survival
PI	Proteasome Inhibitors
PiC	Powder in Capsule

PK	Pharmacokinetics
PR	Partial Response
QD	Once Daily
QTc	QT Interval Corrected
QTcF	QT Interval Corrected using Fridericia's Formula
RDE	Recommended Dose and Regimen for Expansion
RRMM	Relapsed Refractory Multiple Myeloma
SAE	Serious Adverse Event
sCR	Stringent Complete Response
SMC	Safety Monitoring Committee
SoA	Schedule of Activities
SPD	Sum of the Products of the Maximal Perpendicular Diameters of Measured Lesions
SPEP	Serum Protein Electrophoresis
STD	Severely Toxic Dose
SUSAR	Suspected Unexpected Serious Adverse Reactions
TEAE	Treatment-Emergent Adverse Event
TRAE	Treatment-Related Adverse Event
ULN	Upper Limit of Normal
UPEP	Urine Protein Electrophoresis
US	United States
VGPR	Very Good Partial Response
WOCBP	Woman/Women of Childbearing Potential

